6. INVESTIGATIONAL PLAN

6.1 Overall study design and plan

This is a non-randomised, non-blinded single arm real world data collection study investigating the safety, tolerability and effectiveness of medicinal cannabis in chronic non-cancer pain subjects. The study will be conducted in a CBMP treatment clinic that has staff experienced at administering and managing the use of CBMP in its current unlicensed status. At time of enrolment, baseline data will be provided by the participant's health care team who is managing their chronic non-cancer pain (to current standard of care) and collected at the clinical study site. This will provide information on the type of chronic non-cancer pain the subject has (including relevant investigations previously conducted) and the types of drugs and non-pharmacological interventions that the subject is receiving or has received. The standard of care treatment and patient management will be determined by the treating physician. All study treatments and/or any change to treatment or management of the disease that occur throughout participation in the study will be recorded as well as being communicated to the subject's GP. Data will be collected either by the Physician during the study visit or via real time collection via an application (ePRO) provided to the subject. Data will be collected retrospectively and prospectively. A sample size of 5000 participants is planned.

[figure not shown]

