Trial subjects will come from patients who have consented to receive treatment at the Harley Street (CPC) clinic. The study will consist of an initiation visit (or call) to allow screening and base line data to be taken and then a follow up visit (or call) every three months thereafter, until the end of the study (after the last subject's 3 years of treatment). Day 0 (baseline) for each subject will be the initiation visit when study treatment is started (first prescription written) (see figure 1). Prior to conducting any data collection, eligibility for enrolment will be assessed, oral consent will be requested for conductance of a genetic test and if appropriate a pregnancy test. A full medical history will be taken to assess suitability for treatment with medical cannabis; focusing on pain aetiology, subject's current standard of care and previous history of medical cannabis, if any use. Each participant will be provided with study documents to allow them to consider whether they want to have their data collected prior to providing written informed consent.

Informed consent documents (consent form and patient information sheet) will be sent to patients at least 2 days prior to the initial consultation to allow patients time to review them. At the time of initial consultation, the clinician will review the documents with the participant again and explain them in detail. If the subject agrees to provide informed consent, the clinician will witness the subject signing the consent form. If this takes place over video conference the clinician will witness and record the signing event. In addition, the subject will provide photographic identification prior to consultation, permitting confirmation of the participants identification at the time of the remote consultation. Free prescriptions for the study regimen will be provided. Subjects will provide saliva samples for genetic single nucleotide polymorphism (SNP) genetic analysis to study the genetic risk of an individual's sensitivity to THC. Subjects will be continuously monitored via real time reporting of patient reported outcomes and cannabis use information delivered by vaporiser and its bluetooth connected mobile phone application. Tolerability-related patient reported outcome

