6.2 Discussion of study design and choice of control groups

The aim of the study is to evaluate whether the addition of medical cannabis to standard of care or at the completion of standard of care is beneficial with regards to pain scores, quality of life, quality of sleep and changes in the use of concomitant medication, as well as being safe and tolerable in subjects suffering from chronic non-cancer pain. The study will utilise a combination of patient reported outcomes and data from the NHS (chronic pain diagnosis, standard of care and health related laboratory tests) to provide a holistic evaluation of the CBMP treatment when combined with standard of care. The patient reported outcomes and NHS data will be transferred into an electronic health repository which will manage their day to day care, provide reports and alerts on the tolerability of the cannabis for each subject and will form the clinical trial database. The matched controls will exclude those potential participants who are consuming illicit cannabis, identified by drug screening. If participants are using illicit cannabis, they will be given the option to stop with a 3-week wash out period. If participants are not willing to cease, they will not be eligible for inclusion in the matched control cohort.

Controls

The analyses of effectiveness will be conducted through comparison with matched controls obtained from NHS sites established to enable data collection from consented subjects receiving standard of care only. Subjects who consent to have their data collected will be asked to provide essential demographic information, details on their chronic pain type, their standard of care and whether they are currently using medical cannabis to help with their pain. This information will be used to match the subject to subjects on the trial. The data collected in the match cohort will mirror the data collected from the CANPAIN minus tolerability data which will not be required.

The CANPAIN study will follow a pragmatic, real-world, 'all-comers' design with wide inclusion criteria, which is designed to result in a more representative sample of the target population and of the matched controls. Baseline characteristics of treated participants may still differ systematically from those of the matched control group and one must account for these systematic differences when estimating the effect of treatment on outcomes.

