6.4.4 Study Drug Discontinuation

Reasons for the discontinuation of study drug may include, but are not limited, to the following:

1. An AE, SAE, drug reaction, or complication, whether related or not to the treatment drug, which precludes continuation of dosing with study drug.
2. Abnormal laboratory results that lead the Investigator to diagnose a poorer prognosis for subject health.
3. Noncompliance with study drug dosing.
4. Noncompliance with study procedures.
5. Subject's right to withdraw consent at any time during the study, with or without a stated reason.
6. Three separate pieces of evidence that the subject is self-administering other cannabis treatments outside of the prescribed study treatment (three strikes rule). Prior users of non-prescription cannabis will be monitored for any indication that they are using non-trial sources of CBMP, through regular explicit questioning and monitoring of patient reported outcome responses.
7. The investigator's opinion that it is not in the subject's best interest to continue study participation.
8. Sponsor's decision to terminate the study.
9. Pregnancy.

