9.5.1.1 Change in baseline pain NRS

The change in baseline pain NRS will be defined as the difference between chronic pain state at the beginning of the study versus the end of the study (after 3 years of treatment).

The primary analysis will be a difference analysis with comparison to appropriately selected matched controls. The endpoint will be tested using a two-sided z-test test to compare results between the prospectively enrolled treated participants and external matched controls. The impact of confounding factors will be reduced as much as possible by including values of important covariates in the model and by performing sub-analyses. Covariates included in the model will be selected based on:

- (1) Base line pain scores
- (2) Cannabis consumption experience and/or
- (3) Cause of chronic pain

A propensity score analysis may also be performed to match subjects between the treated and matched control groups. The propensity score is the probability of treatment assignment conditional on observed baseline characteristics. Propensity score matching entails forming

matched sets of treated and untreated participants who share a similar value of the propensity score (Rosenbaum PR & Rubin DB, 1983a and 1985).

Secondary measure outcome variables

Descriptive statistics will be presented for Quality of life changes, sleep NRS changes, Anxiety changes, confusion changes, dizziness changes, and changes in the use of concomitant medicines. Change from baseline to a number of analysis time points (including 12 months) will be assessed. Repeated measures analyses will be undertaken to allow for the evaluation of outcomes at any timepoint. In addition, multi-state modelling (MSM) will be undertaken to assess time-varying confounds. These will be described in detail in the SAP.

A comparison between treated subjects and matched control may be performed if similar endpoints are collected in both databases. Time to event analysis, multiple regression analysis for continuous and/or categorical outputs and/or propensity score analysis may be performed as appropriate.

To deal with missing data in subjects over the 3 year period, patterns of missingness will be evaluated including missing completely at random (MCAR), missing at random (MAR) or missing not at random (MNAR) will be assessed, this will be described in detail in the SAP.

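### The cannabis item stated for controls is current use while treated patients give previous use, and the sources for pain type and standard of care are not aligned, so like-with-like matching is not assured

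*Protocol*

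**What the plan says.** All of this is in Appendix 1, the draft CANPAIN protocol.

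**Treated patients (6.1).** At enrolment, "baseline data will be provided by the participant's health care team who is managing their chronic non-cancer pain". These data cover "the type of chronic non-cancer pain the subject has (including relevant investigations previously conducted) and the types of drugs and non-pharmacological interventions" received now or in the past. The clinic also takes a full medical history that includes pain aetiology, current standard of care and "previous history of medical cannabis, if any use". Section 6.6.1 adds a medical questionnaire at Day 0.

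**Controls (6.2).** Consenting subjects at NHS sites who receive standard of care only are "asked to provide essential demographic information, details on their chronic pain type, their standard of care and whether they are currently using medical cannabis" for their pain. The text continues: "This information will be used to match the subject to subjects on the trial". The next sentence says the control data will mirror the CANPAIN data, tolerability excepted. Potential controls found by drug screening to use illicit cannabis are excluded unless they stop and complete a 3-week wash-out.

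**Use in the analysis.** Section 9.5.1.1 names three bases for choosing covariates for the primary comparison: baseline pain, then "Cannabis consumption experience and/or" cause of pain. Section 9.1 lists prior cannabis use and standard of care among the exploratory subgroups and pain type among those of special interest. Section 6.4.4 expects past users among treated patients: "Prior users of non-prescription cannabis will be monitored" for use of other sources.

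**The concern.** The comparison is not randomised. Matching and covariate adjustment are the only design features that protect it from confounding. Both work only if a variable means the same thing in the two cohorts. If cannabis history is past use in one cohort and present use in the other, matching or adjusting on it does not equate the cohorts on past exposure. If pain type is recorded by a clinician in one cohort and reported by the patient in the other, two people matched as having the same type may not have it. Balance tables built on the recorded values can look satisfactory in either case. Section 6.2 acknowledges unmeasured confounding as a limitation, but does not mention a matching variable measured differently by cohort. A later analysis plan cannot recover a history that was never asked for.

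**Working it through.** **Step 1: the items side by side.**

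| Variable | Treated (6.1, 6.6.1) | Control (6.2, Controls) |
|---|---|---|
| Cannabis | Previous medical use, by history | Current medical use, asked of the subject |
| Pain type | Health care team, plus history and Day 0 questionnaire | Asked of the subject |
| Standard of care | Health care team, plus history and Day 0 questionnaire | Asked of the subject |

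The cannabis row differs in what is measured. The other two rows differ in the named source, with partial overlap because treated patients also give a history.

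**Step 2: can the control item serve the analysis?** Controls are to receive standard of care only, so the answer to the current-use question should be no for nearly all who are kept. An item with almost no variation cannot act as a measure of cannabis experience or define a prior-use subgroup. Past users can nevertheless be controls, because 6.2 admits illicit users after a wash-out. No baseline item stated for controls records past use.

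**Step 3: the planned effect, for scale.** Section 9.2 assumes 25% improving in controls. Its wording on 28% is ambiguous; it is read here as 28% in treated patients. For a two-sided 5% test:

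n = [1.96 √(2 × 0.265 × 0.735) + 0.842 √(0.25 × 0.75 + 0.28 × 0.72)]² / 0.03² = 3397 per group for 80% power.

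With 3600 per group, power is 82.2%, and 3600 / (0.90 × 0.80) = 5000. Both agree with the plan. Reading 28% as a relative increase (0.25 × 1.28 = 32%) would give power above 99.9%, so 25% v 28% is the more natural reading. The planned difference is therefore 3 percentage points. The sample size itself does not depend on the present point.

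**Step 4: illustration for cannabis history.** The document gives no inputs, so these are assumptions.

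Shift = imbalance in past use between matched cohorts × difference in responder rate between past users and others.

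| Imbalance | 5-point difference | 10-point | 15-point |
|---|---|---|---|
| 10% | 0.5 | 1.0 | 1.5 |
| 20% | 1.0 | 2.0 | 3.0 |
| 30% | 1.5 | 3.0 | 4.5 |
| 40% | 2.0 | 4.0 | 6.0 |

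**Step 5: illustration for pain type.** Assume two types, a correct record in treated patients, and self-report in controls with sensitivity and specificity both equal to s (0.70 to 0.95). Assume also that half of the control pool has the first type, and that a share p of treated patients has it (30% to 70%). After exact matching on the recorded type, the true share in controls is p·s + (1 − p)(1 − s).

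- p = 0.30, s = 0.70: 0.21 + 0.21 = 0.42, an imbalance of 12 points. With a 15-point difference in responder rate the shift is 1.8 points.
- p = 0.30, s = 0.95: 0.285 + 0.035 = 0.32, an imbalance of 2 points. With a 5-point difference the shift is 0.1 points.
- p = 0.50, any s: no imbalance and no shift.
- p = 0.70 gives the same sizes as p = 0.30 with the opposite sign.

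The range is 0 to 1.8 points in either direction.

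**The case against.** The strongest reply is the mirror sentence. It can be read as governing the whole control dataset, with the list before it only summarising what subjects say at entry. Nothing limits the control data to the listed items. The sources also overlap: treated patients give a history and complete a questionnaire, and 6.2 names NHS data for pain diagnosis and standard of care. Section 9.1 gives a wider set of matching variables, cites a reply not included in the document, and leaves full details to the SAP. Cannabis experience is only a candidate covariate. Finally, Appendix 1 is a draft, the feasibility study has no control group, and section 2 of the feasibility protocol says the next application will address concerns about it.

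Much of this stands for pain type and standard of care. A reader might infer that those two variables come solely from clinicians in one cohort and solely from self-report in the other, so that matching certainly fails. The documents do not support that. Nor do they support saying that past non-medical use is recorded nowhere. Section 6.1 takes earlier cannabis experience into account in prescribing, 6.4.4 presupposes that past users are known, and controls are drug-screened.

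It does not remove the cannabis point. A general promise to mirror does not settle specific items that differ in the same paragraph. A drug screen shows recent use, not history. The NHS-data sentence concerns evaluation of the cannabis treatment and does not say that it covers controls. The wording of a baseline question has to be fixed before collection. The draft status makes this a convenient time to correct it.

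**Conclusion.** The point holds in a limited form. Section 6.2 promises mirrored data but lists a control cannabis item with a different time frame from the treated item in 6.1. As written, that item cannot serve the covariate in 9.5.1.1 or the subgroup in 9.1. The difference in stated source for pain type and standard of care is a lesser matter: it is a risk to like-with-like matching, not an established failure.

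The size of any bias is unknown. The 0.5 to 6.0 points for cannabis history and 0 to 1.8 points for pain type rest entirely on assumed imbalances, accuracies and responder differences. They show only that the first could reach the 3-point planned difference and that the second, on these inputs, stays below it and may be nil. No corrected sample size follows.

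**What to change.** In section 6.2 of the CANPAIN protocol:

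1. Ask both cohorts one identical Day 0 question on any past cannabis use, prescribed or not, with recency. Use it for matching and as covariate (2) in 9.5.1.1. The current-use question to controls can stay as an eligibility check.
2. Name one source and one coding list for pain type and standard of care in both cohorts. This can be the NHS record, since controls are recruited at NHS sites, or the same Day 0 questionnaire, since treated patients already complete one.
3. Reconcile the mirror sentence with the listed items so that it is true as written.

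The cost is protocol wording and one shared form. Using the NHS record would add a small abstraction effort at the sites.

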7.2 Exclusion Criteria

1. Pregnant or lactating females or females who are planning a pregnancy during the study;
2. Positive pregnancy test at time of joining the clinic;
3. Major organ failure, renal, lung or liver failure;
4. Participants having active liver disease or unexplained persistent elevation of serum transaminases > 3 times the upper limit of normal;
5. Participants with a creatinine clearance < 60mL/min;
6. History of cardiac or respiratory failure;
7. History of recent myocardial infarction or poorly controlled ischaemic heart disease;
8. Severe respiratory disease (e.g., GOLD 3 for COPD or asthmatics requiring high doses of oral corticosteroids);
9. History or presence of alcohol or substance abuse, including analgesics used as standard of care;
10. Participation in a clinical trial of an investigational medicinal product;
11. With any known or suspected history or family history of schizophrenia, or other psychotic illness; history of severe personality disorder or other significant psychiatric disorder disorders other than depression associated with their underlying condition;
12. Known hypersensitivity to cannabis or allergy to cannabis or CBMP; and
13. Currently taking cannabis and does not agree to a 3 week wash out period.

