6.4.2 Exclusion criteria

Study exclusions will be assessed by the study clinician in light of established cannabis restrictions. However, in general participants meeting any of the following exclusion criteria will not be included in the study;

1. Pregnant or lactating females or females who are planning a pregnancy during the study;
2. Positive pregnancy test at screening;
3. Major organ failure, renal, lung and liver failure;
4. Participants having active liver disease or unexplained persistent elevation of serum transaminases > 3 times the upper limit of normal;
5. Participants with a creatinine clearance < 60mL/min; History of cardiac or respiratory failure;
6. History of cardiac or respiratory failure;
7. History of recent myocardial infarction or poorly controlled ischaemic heart disease;
8. Severe respiratory disease (e.g., GOLD 3 for COPD or asthmatics requiring high doses of oral corticosteroids).
9. History or presence of alcohol or substance abuse, including analgesics used as standard of care.
10. Participation in a clinical trial of an investigational medicinal product;
11. With any known or suspected history or family history of schizophrenia, or other psychotic illness; history of severe personality disorder or other significant psychiatric disorder other than depression associated with their underlying condition.
12. Known hypersensitivity to cannabis or allergy to cannabis or CBMP and
13. Direct employee of the study site.

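### Draft CANPAIN section 6.2 uses current medical cannabis use as matching information and excludes only illicit use, so a control already on prescribed cannabis can enter a standard-of-care-only comparator

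*Protocol*

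**What the plan says.** The statements about controls stand close together in Appendix 1, section 6.2.

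- NHS sites are set up for "data collection from consented subjects receiving standard of care only".
- Those subjects are asked, among other things, about being "currently using medical cannabis to help with their pain. This information will be used to match the subject to subjects on the trial".
- On exclusion, the section says: "The matched controls will exclude those potential participants who are consuming illicit cannabis, identified by drug screening". The next sentence adds: "If participants are using illicit cannabis, they will be given the option to stop with a 3-week wash out period". Prescribed cannabis is not mentioned as an exclusion.

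On the treated side, Appendix 1 section 6.1 draws subjects from consented clinic patients and sets Day 0 at the first prescription. Before data collection, "oral consent will be requested for conductance of a genetic test and if appropriate a pregnancy test"; no cannabis test is named there. The CANPAIN exclusions (synopsis and 6.4.2) contain no criterion on current cannabis use, and their last item is "13. Direct employee of the study site". In the feasibility protocol the item with the same number is "Currently taking cannabis and does not agree to a 3 week wash out period". The clinical pathway in section 2 of the feasibility protocol requires a patient who fails a urine cannabis test to stop for 3 weeks and test negative before treatment.

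**The concern.** The question CANPAIN asks is whether cannabis added to standard of care does better than standard of care alone. Current medical cannabis use is that exposure. For a control it should be a reason for exclusion, not a characteristic on which to find a partner. As section 6.2 is worded, a control on prescribed cannabis passes the stated exclusion and has cannabis status fed into the match. Exposed controls who respond would pull the comparison towards no difference, and the planned difference leaves little room for that.

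A second point concerns baseline. Section 6.2 states that all analyses use change from baseline. If one cohort's baseline pain is measured off cannabis and the other's is not, the change does not mean the same thing in both. The passages that govern this do not agree with each other.

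**Working it through.** **1. Who can be a control.** Section 6.2 gives one description (standard of care only), one exclusion (illicit cannabis) and one matching item (current medical cannabis). The description would rule out a prescribed user, the exclusion does not, and the matching item presupposes that such users may be present. Section 9.1 plans 1-1 optimal matching and says only that certain covariates may be matched exactly. A variable used for matching therefore does not by itself act as an exclusion.

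**2. When the treated subject's status is taken.** Section 6.1 puts baseline at the first prescription. Stage 4 of Figure 1 has patients invited to join while already in the clinic's treatment phase, with the study protocol followed from then on.

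- Status taken at Day 0, with treated subjects cannabis-negative: matching would tend to select non-users.
- Status taken at joining during treatment: every treated subject is a current user, and matching would favour exposed controls.

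The document does not say which applies.

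**3. The plan's own figure.** Inputs from section 9.2: control rate 25%; 28%, read as the treated rate; 3600 per group; two-sided z-test at 5%.

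- Mean rate = (0.25 + 0.28)/2 = 0.265
- SE under no difference = √(2 × 0.265 × 0.735 / 3600) = 0.01040
- SE under the alternative = √((0.25 × 0.75 + 0.28 × 0.72) / 3600) = 0.01040
- Power = Φ((0.03 − 1.96 × 0.01040) / 0.01040) = Φ(0.92) = 82.2%

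This agrees with the stated minimum of 80%, for which 3397 per group would suffice. The inflation also reproduces: 3600 / (0.9 × 0.8) = 5000. Reading the 28% as a relative increase (25% v 32%) would need only 652 per group, so it does not fit 3600.

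**4. Effect of exposed controls.** Let c be the share of controls on cannabis, and suppose they improve at the treated rate. The control rate is then 0.25 + 0.03c and the difference 0.03(1 − c). The documents do not give c; the values below are assumptions.

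| c | Control rate | Difference (points) | Power at 3600 per group | n per group for 80% |
|---|---|---|---|---|
| 0% | 25.00% | 3.00 | 82.2% | 3397 |
| 3% | 25.09% | 2.91 | 79.9% | 3614 |
| 5% | 25.15% | 2.85 | 78.2% | 3770 |
| 10% | 25.30% | 2.70 | 73.6% | 4209 |
| 20% | 25.60% | 2.40 | 63.3% | 5346 |

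If those controls instead improve at 25%, for example because they are already stable on cannabis, nothing is lost at any c. If they improve less often than that, the observed difference grows. The table shows the unfavourable case, not a forecast.

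**5. Test and wash-out.**

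| Place | What it provides |
|---|---|
| Feasibility protocol, section 2 (clinical pathway) | Urine cannabis test for clinic patients; 3-week stop and negative test before treatment |
| Feasibility exclusion 13 | 3-week wash-out for current users |
| Appendix 1, 6.2 | Drug screen and optional 3-week wash-out, written for controls |
| Appendix 1, synopsis, 6.1 and 6.4.2 | No cannabis test or criterion named for treated subjects |

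Section 2 of the feasibility protocol also says that the tests required of patients follow Appendix 1, whose visible text for treated subjects names no cannabis test.

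**The case against.** The strongest reply is that the comparator is sound in intent. Controls are to receive standard of care only. The general list of matching variables in section 9.1 does not name current cannabis use. Section 9.5.1.1 uses cannabis consumption experience as a covariate, which is reasonable. Appendix 1 is a draft, section 2 of the feasibility protocol says the later application will address the ethics committee's concerns about the control group, and matching detail is left to the SAP. All of that stands and lowers the weight of the point. It does not remove the conflict inside section 6.2, because an analysis plan cannot exclude from enrolment a control whom the protocol admits.

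A reader might infer four stronger things that the documents do not support.

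- *Only controls are washed out.* This is true of the visible text of Appendix 1 alone. The clinic pathway imposes a wash-out and a negative test before treatment, and the treated cohort comes from clinic patients. Only stage 4 of Figure 1 is legible, so a test at an earlier stage cannot be ruled out.
- *Controls are checked once and then left unmonitored.* No passage says so. Section 6.2 says control data mirror those of CANPAIN apart from tolerability. The three-strikes rule in 6.4.4 concerns stopping study drug and could not apply to controls.
- *Matching necessarily favours exposed controls.* That depends on when status is taken, which is not fixed.
- *The change in pain is biased.* Neither the size nor the direction is determined by anything in the document.

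**Conclusion.** The point holds as a conflict within section 6.2: a standard-of-care-only comparator is described, but prescribed cannabis is not excluded and current medical cannabis use is matching information. The consequence is a risk of dilution. Against a planned 3-point difference, power falls from 82% to about 80%, 74% and 63% with 3%, 10% and 20% of controls on cannabis. This rests on three assumptions: the share c, a full treated-rate response in those controls, and the reading of 28% as the treated rate.

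The test and wash-out passages contradict each other across the two protocols and need reconciling; they do not establish that the cohorts will differ at baseline. The matter should be fixed before the CANPAIN resubmission. The feasibility study has no control arm, and its own objectives are not affected.

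**What to change.** In Appendix 1, section 6.2:

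1. Remove current medical cannabis use from the matching information and make current use of any cannabis, prescribed or illicit, a reason for exclusion from the control cohort.
2. Match on cannabis experience before baseline, in line with the covariate in 9.5.1.1, and state the time at which it is recorded in each cohort.
3. Record non-study cannabis use in both cohorts during follow-up, and report the pain comparison with and without controls who start cannabis.

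Separately, reconcile the feasibility protocol (section 2 and exclusion 13) with Appendix 1 (synopsis, 6.1, 6.2 and 6.4.2), so that baseline pain is measured under the same cannabis status in both cohorts. Which testing or wash-out rule applies is for the sponsor and clinicians to decide.

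The cost is amended wording in a draft, one questionnaire item, and some controls becoming ineligible, which may make it harder to reach 5000.
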